6.4.6 Physical examination

A complete physical examination should be completed by a physician or any qualified licensed staff at the randomization visit (Week 1, Visit 2), and Week 14 (follow-up visit), and recorded by body system on the appropriate sections of the source documentation and eCRF.

The complete physical examination will include assessments of the following: height, weight, and calculated BMI, general appearance, skin, head, neck (including eyes, ears, nose, and throat), lymph nodes, thyroid, musculoskeletal/extremities (including spine), cardiovascular, lungs, abdomen, and neurological systems. Complete physical examination data to be recorded on the eCRF will include: 1) normal/abnormal and 2) a description of the abnormalities.

Height will be measured in centimeters (cm) and weight will be measured in kilograms (kg) with the patient wearing light clothing and without shoes.

6.4.7 ECG

6.4.7.1 Resting digital 12-lead ECG

Digital ECGs for all patients at all sites will be conducted at the sites using a machine provided by the central ECG laboratory [REDACTED] and will be transmitted to [REDACTED] (Section 13.1). Digital ECG will be performed at specified study visits at screening, prior to start of infusion (T_0), and at the end of the infusions (T_1). Table 8 displays a summary of the timing of study-related ECG assessments.

The ECG at T_0 of Visit 2 (Day 1) will be considered the baseline value.

Table 8 Schedule of ECG assessments after enrollment

Week	Visit	Infusion number	ECG assessments	
			Predose (T_0)	Post dose (T_1)
1	2	1	x	x
1	4	3		x
3	10	9		x
6	13	12		x
12	16	15		x

Digital ECGs will be obtained after the patient has been resting in a semi-recumbent position for at least 10 minutes.

All digital ECGs will be documented by recording date, time, heart rate, QRS duration, PR interval, RR interval, QT, and QTcF. QTcF intervals will be calculated using the Fridericia formula (Puddu et al 1988).

If indicated, additional ECG assessments can be made at the discretion of the investigator. These assessments should be entered as an unscheduled assessment on the appropriate eCRF.

The investigator will judge the overall interpretation as normal or abnormal. If abnormal, it will be decided as to whether or not the abnormality is clinically significant or not clinically significant and the reason for the abnormality will be recorded on the eCRF. Abnormal values shall not be recorded as AEs unless deemed clinically significant.

Quality assurance of the ECG waveform and patient demographics will be conducted by a central laboratory operator at [REDACTED]. Digital ECGs will be processed through a computer interpretation program and then reviewed, first by an ECG analyst and then by a board-certified cardiologist. Results will be faxed and a hard copy report mailed to the site.

6.4.8 Vital signs

6.4.8.1 Pulse and blood pressure

Supine BP and pulse rate will be measured at the screening visit, randomization (Day 1), and at each scheduled weekly visit, ending at Week 14 (Table 4).

An appropriately sized cuff will be used to obtain systolic and diastolic BP. Orthostatic BP should be assessed at baseline and at least 1 hour or 3 hours after the end of the infusion. The assessment will be done first with the patient in the supine position for 3 minutes and again within 3 minutes of the patient attaining a standing position. Standing and supine BP and pulse rate should be measured with the right arm at heart level.

6.4.8.2 Body temperature

Oral body temperature will be measured in degrees centigrade (°C) using an automated thermometer and will be taken at the screening visit, randomization (Day 1), and at each scheduled weekly visit (Table 4).

6.4.9 Other safety assessments

6.4.9.1 Medical, surgical, and medication history

A detailed medical surgical history including medication history will be recorded for each patient during the screening visit (Visit 1). Significant medical conditions that have occurred within the past 12 months (1 year) or conditions that are ongoing (ie, headache, backache, indigestion) will be recorded in the eCRF (Table 4).

The medication history must identify any known drug allergies, presence or history of drug abuse, and use of chronic medications.

6.4.9.2 Pregnancy test

A serum pregnancy test will be performed on all females at the screening visit (Visit 1). A negative urine pregnancy test is required each visit prior to the administration of IP for all WOCBP. If a pregnancy test is found to be positive at any time, the patient will not be able to continue participation in the study (see Table 4 for the timing of pregnancy testing and Section 13.3 for procedures in case of pregnancy).

6.4.9.3 Urine drug screen

A urine sample will be evaluated only during the screening visit. Additional evaluations may be performed at the discretion of the investigator. These additional assessments can be performed using a dipstick method such as a Clinical Laboratory Improvements Amendment (CLIA)-Waived dipstick, but if positive, the test should be confirmed by a full urine drug screen.

The sample will be tested for the drugs of abuse including methamphetamines (including ecstasy), benzodiazepines, cocaine and/or metabolites, amphetamines, THC, opiates, PCP, barbiturates, and ethanol (Table 7).

Patients who have a positive UDS for a drug(s) legally available by prescription must provide evidence of the prescription for the drug(s). Patient can in some cases be re-tested and may be eligible to continue in the study, see exclusion criterion 9 for details.

Note: Although the results of the UDS must be documented in the patient's file, the results will not be collected on the eCRF and will therefore not be recorded in the study database.

6.4.9.4 Serology testing

Serology testing for HIV antibody, HBsAg, and HCV antibody will be performed on all patients during the screening visit only (Table 4). If a test is positive, the patient will not be allowed to participate in the study.

Note: Although the results of the HIV and hepatitis serology testing must be documented in the patient's file, the results will not be collected on eCRFs and will therefore not be recorded in the study database.

6.4.9.5 CogState (cognitive functioning measurement)

The CogState battery selected for this study is a collection of 4 highly sensitive computerized neurocognitive tests assembled to meet the objectives of this study for brevity (12 to 15 minutes), sensitivity to areas previously reported to be affected by ketamine, another NMDA antagonist (psychomotor speed, attention, working memory, and short-term memory) and is appropriate for a depressed population. The tasks used (Detection task [DET], Identification task [IDN], One-card Learning task [OCL] and One-back task [OBK]) are all language free with the exception of test instructions, which are provided in the local language. Patients practice each test twice, during the screening visit, (or more frequently if required to assure complete understanding of the requirements of each task). If both practice tests could not be completed at the screening visit or if task understanding is not achieved at the screening visit, it is acceptable to administer one or more practice tests at the randomization visit. The patient must demonstrate complete understanding of each task prior to baseline testing. No sedatives, hypnotics, benzodiazepines, or sedating antihistamines are permitted within 12 hours of cognitive testing.

The CogState battery is presented on a laptop computer, with 2 external response buttons attached. At the beginning of each battery, a training task, called the "Fixed Response Mapping Task" is conducted. The purpose of this task is to train the patient on which is the "Yes" button and which is the "No" button. In the unlikely event that a patient has difficulty learning this, it is acceptable for study staff to place a small card or post-it note with the words No and Yes near the left and right buttons respectively.

On each trial of each cognitive task, a single playing card stimulus is presented in the center of the computer screen. The value, color, and suit of each playing card are determined according to the requirements of each cognitive task. At the presentation of each playing card stimulus patients are required to respond either "Yes" or "No" by pressing the designated button. At the beginning of each task, the rules are presented on the computer screen. They are also read out by the administrator to the participant. This is followed by a short practice of the task.

Once the practice are complete, the actual task begins. On each assessment, the 4 tasks are presented in the same order (ie, that given above). At the beginning of each task, participants are instructed to “respond as quickly and as accurately as possible.” The CogState tests must be administered at designated visits prior to infusion.

6.4.9.6 Columbia-Suicide Severity Rating Scale (C-SSRS)

The C-SSRS is a unique, simple and short method of assessing both behavior and ideation that tracks all suicidal events, and provides a summary of suicidality (Posner et al 2007). It assesses the lethality of attempts and other features of ideation (frequency, duration, controllability, reasons for ideation and deterrents), all of which are significantly predictive of completed suicide.

The C-SSRS will be administered at the screening visit and at each scheduled visit throughout the study by a trained rater. The trained rater will record the clinical observation on the scale, which will be used as the source document. If at all possible, the same individual should perform the assessment at each visit to reduce scoring variability. In the event the primary rater is not available, a designated back-up rater who meets the same qualifications may perform the C-SSRS.

The C-SSRS must be administered at designated visits after the infusion.

6.4.9.7 Clinician Administered Dissociative States Scale (CADSS)

The CADSS is a 23-item self-report scale (Bremner et al 1998). It is a reliable, valid self-report instrument designed to assess state symptoms of dissociation in response to a specified stressor. Severity of each dissociative symptom can range from 0 (not present) to 4 (extreme). The CADSS must be administered at designated visits after the infusion.

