1.1.2.2 Pharmacokinetics and product metabolism in humans

Following a constant iv infusion of up to 1 h, AZD6765 maximum plasma concentration level is reached at the end of infusion. Thereafter, the plasma concentration levels initially decrease rapidly followed by a slower decrease; hence, the disposition of AZD6765 can be characterized as multiphasic with an initial distribution phase and a later elimination phase. AZD6765 is slowly cleared from the body with a total clearance of about 9.2 L/h (0.13 L/h/kg) and a terminal elimination half-life that range from 11 hr to 14 hr. The PK of AZD6765 is linear in the dose range studied (1 mg to 160 mg) and is similar between elderly subjects and healthy adult males as well as between Japanese and Caucasian subjects. Since renal clearance is one of the major routes of elimination (accounting for approximately one quarter of total clearance), mild-to-moderate renal impairment had some effects on the PK of AZD6765.

Consistent with being a low clearance compound, AZD6765 showed a low degree of metabolism in humans. The unchanged parent compound accounted for >65% of the area under curve 0 hr to 24 hrs ($AUC_{(0-24)}$) of the total plasma radioactivity. The major metabolites in the plasma were glucuronic acid conjugates of carbamic acid, para-hydroxy and para-hydroxycarbamic acid metabolites.

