- ^h A negative urine pregnancy test result is required prior to each dose of IP. Pregnancy tests will be administered and processed at the study site.
- ⁱ These measures will always be administered **prior to** any IP infusion.
- ^j At the screening visit, practice CogState is administered for training. The tests should be given twice (or more frequently if required to assure complete understanding of the requirements of each task).
- ^k CADSS will be administered at designated visits **after** infusion.
- ^l Patients must remain on site at randomization and the last infusion visit for at least 3 hours after the end of the infusion and at least 1 hour after the end of infusion at other scheduled infusions. Patients should be queried about any AEs and assessed for ability to leave the clinic, including their ability to drive or access to alternative transportation (see Section 5.1), prior to dismissal from the clinic at each infusion.
- ^m Weeks 1 through 3 post randomization-dose administration 3 times a week; Weeks 4 through 6 – dose administration once weekly; Weeks 8, 10, and 12 – dose administration once weekly. No drug administration will take place on Week 7, Week 9, and Week 11.

Figure 1Dosing flow chart

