6.2.1.2 Randomization visit (Visit 2)

Prior to the randomization visit, adequate documentation must be in place to confirm that the patient meets modified ATHF inclusion criteria of inadequate response to at least 2 previous antidepressant treatments of adequate dose and duration. In addition, results from all laboratory assessments conducted at the screening visit should be available and confirm that the patient continues to meet clinical and safety criteria for inclusion.

At the randomization visit, the QIDS-SR-16 will be administered first. Prior to conducting any further procedures, the QIDS-SR-16 should be scored (without review by the investigator) and if the inclusion criterion score of ≥ 19 is not met, no further study procedures are to be conducted and the patient will not be randomized. At no time may the patient be informed of the inclusion criterion score on the QIDS-SR-16. If the QIDS-SR-16 criterion is met, the HAM-D-17 interview will be conducted and the CGI-S will be completed to determine whether the patient meets the inclusion criteria of a HAM-D-17 total score ≥ 24 and CGI-S ≥ 5 . If these criteria are not met, no further procedures are to be conducted and the patient will not be randomized. If these criteria are met, the patient is randomized and the remaining clinical and laboratory assessments are conducted in accordance with Table 4.

The MADRS, CGI-S, S-STS, HAM-A, SDS, and Cogstate are conducted prior to the first infusion. After the first (and last) infusion, the patient must remain in the clinic for at least 3 hours after the infusion (T_4) during which time AEs are collected, and CADSS and C-SSRS are administered. Vital signs and orthostatic BP are measured at every infusion at multiple time points: T_0 , T_1 (vital signs only), and either at least 1 hour (T_2) after the end of infusion (all indicated visits, except for Visits 2 and 16), or, at least 3 hours (T_4) after the end of infusion (applies to Visits 2 and 16, which corresponds to first and last infusions).

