6.3 Efficacy

6.3.1 Sequence of clinical rating assessments

Table 4 lists all clinical and laboratory assessments to be conducted at the screening visit and all subsequent visits. The following “priority order” among clinical ratings will be in effect for all visits after the screening visit.

Pre-infusion

- QIDS-SR-16
- S-STS (self report)
- MADRS
- HAM-A
- SDS
- CGI-S
- CGI-I
- CogState

Post-infusion

- C-SSRS (conducted by the investigator after reviewing and signing S-STS during visits when both instruments are used)
- CADSS

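### The CADSS, a state measure of dissociation, has no fixed time after the infusion and no stated recall period, and is ranked behind the C-SSRS, so its readings may be diluted and hard to compare across visits

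*Protocol*

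**What the plan says.** Section 6.4.9.7 describes the CADSS as "designed to assess state symptoms of dissociation in response to a specified stressor" and then fixes its timing: "The CADSS must be administered at designated visits after the infusion". Table 4 note k says the same ("CADSS will be administered at designated visits", after infusion), and the weekly text in Section 3.1.2 adds nothing more precise.

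Section 6.3.1 gives a priority order that "among clinical ratings will be in effect for all visits after the screening visit". Its post-infusion part has two entries: the C-SSRS, preceded by review and signing of the S-STS where both are used, and then the CADSS.

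For the randomization visit, Section 6.2.1.2 says: "After the first (and last) infusion, the patient must remain in the clinic for at least 3 hours after the infusion", "during which time AEs are collected, and CADSS and C-SSRS are administered". Section 3.1.2 (Weeks 4 to 6) and Table 4 note l set a minimum stay of 1 hour at Visit 13. Table 4 marks the CADSS at Visits 2 and 13 only.

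On exposure, Section 1.1.2.2 says "AZD6765 maximum plasma concentration level is reached at the end of infusion" and describes a fast early decline followed by a slower one. The CADSS is a safety objective (Section 2.3). The synopsis and Sections 11.1.5 and 11.2.6.2 define its outcome as change from baseline at each scheduled assessment.

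**The concern.** A scale that records a present state gives a reading that depends on when it is taken. If the effect follows plasma concentration, it should be strongest near the end of infusion, and the 6.3.1 order puts another interview between that moment and the CADSS. Nothing then limits how much later the rating may be made, and the protocol does not ask for its time.

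Two things are at stake. First, late ratings would pull a real drug-placebo difference toward zero. For a safety outcome that is false reassurance, and the benefit-risk case in Section 1.4 leans on this drug having fewer psychotomimetic effects than ketamine. Second, a difference between the first and twelfth infusions could reflect when patients were rated and not tolerance or accumulation. Unrecorded times would also weaken any use of CADSS data in the exploratory PK/PD work foreseen in Section 11.4.

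**Working it through.** The protocol states no figure that depends on CADSS timing, so there is nothing to reproduce. The check sets the timing rules side by side.

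**1. Time anchors at the two CADSS visits in Table 4** (notes c, e, k, l; Section 6.4.7.1; Table 9)

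| | Visit 2 | Visit 13 |
|---|---|---|
| Minimum stay after end of infusion | 3 h (T4) | 1 h (T2) |
| Vital signs | T0, T1, T4 | T0, T1, T2 |
| ECG | T0, T1 | T1 |
| PK, from start of infusion | 0, 50 min, 2, 3, 4 h | 0.5, 1.25, 2 h |
| CADSS | after infusion | after infusion |

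The other measures at these visits that could vary with exposure have a clock point. The CADSS does not. The minimum stays differ by a factor of 3 / 1 = 3, and neither has an upper limit. Section 6.2.2.6 requires the C-SSRS before discharge; no such general rule is given for the CADSS, although Section 6.2.1.2 places it within the stay at Visit 2.

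**2. What the stated half-life can and cannot show.** The only half-life given is terminal, 11 to 14 hours (Section 1.1.2.2). With fraction remaining = 2^(−t/h):

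- t = 1 h: 2^(−1/11) = 0.939 and 2^(−1/14) = 0.952.
- t = 3 h: 2^(−3/11) = 0.828 and 2^(−3/14) = 0.862.

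On the terminal phase alone, about 94 to 95% of the end-of-infusion level would remain at 1 hour and 83 to 86% at 3 hours. The true level is lower because of the rapid early phase, which is not quantified. These are therefore upper limits on concentration and say nothing direct about symptoms. The size of the loss cannot be derived.

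**3. The visit schedule.** Table 4 has the CADSS at Visits 2 and 13. Section 3.1.2 also describes post-infusion CADSS ratings under Weeks 2 to 3 and Weeks 7 to 12, where Table 4 marks none. Section 6.2.1.2 names the first and last infusions before mentioning the scale, and the last infusion is Visit 16. These places do not agree.

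**4. The baseline.** Table 4 schedules no CADSS before the first infusion. Let e2 and e13 be the drug effects on the score at Visits 2 and 13. If the Visit 2 score serves as baseline, the expected drug-placebo difference in change at Visit 13 is e13 − e2. If the two effects are equal, this is zero however large they are. Moving the rating nearer the peak would, if anything, increase e2, so a timing change alone does not repair this outcome.

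**The case against.** A reader might infer that a rating made late in the stay finds a patient who has already recovered, or might assume a short half-life for symptoms and put a percentage on the loss. The protocol supports neither. It gives no rate of decline for dissociative symptoms and does not quantify the early fall in concentration. The one clock time it gives for the class effect, in Section 1.4, puts ketamine's euphoric and psychotomimetic effects within 2 to 4 hours of administration, so a rating during the stay may well catch an effect.

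Other points on that side carry weight:

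- The scale is tied to a stressor and its recall period is not stated. If the form asks about the infusion period, much of the risk goes away.
- The 3-hour and 1-hour figures are minimum observation stays; no CADSS window exists. Since the same order applies at both visits, a site could rate at the same point each time.
- Loose timing is common to all blinded arms, so the expected consequence is dilution and not confounding between arms.
- The CADSS is summarised descriptively (Section 12.2.4), and questioning about adverse events before release is a partial backstop.

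These points limit the size and certainty of the harm. They do not supply a time anchor, a recall period or a recorded time, and they do not explain why the CADSS is ranked after the C-SSRS.

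**Conclusion.** The point stands as a design weakness in a safety measure. CADSS timing is uncontrolled, and the stated order moves it away from the end of infusion. Compliant sites could rate at very different points, which may dilute a drug-placebo difference and blur the comparison of Visits 2 and 13. This rests on two assumptions: that dissociative symptoms broadly follow plasma concentration, and that the form does not already cover the whole infusion period. The protocol settles neither. The size is unknown and the effect is not certain to be missed. The primary efficacy analysis is not affected. The conflicting visit schedules and the missing pre-infusion rating belong to the same repair, because better timing without a sound baseline would still leave the change score uninterpretable.

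**What to change.** - In Section 6.3.1, Section 6.4.9.7 and Table 4 note k, make the CADSS the first post-infusion rating, in a short fixed window starting at T1 and identical at every CADSS visit.
- State that symptoms are rated for the period since the infusion began, and record the actual time of rating.
- Keep the C-SSRS before discharge, as Section 6.2.2.6 requires.
- Reconcile the CADSS visits across Table 4, Section 3.1.2 and Section 6.2.1.2.
- Do not use the post-infusion Visit 2 score as baseline. Either compare post-infusion scores between arms at each CADSS visit, or add a pre-infusion CADSS at Visit 2. Align the outcome definition in the synopsis and Sections 11.1.5 and 11.2.6.2 with the choice.

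The cost is mainly wording. Vital signs and the ECG already bring staff to the patient at T1 at Visits 2 and 13. The downside is a few more minutes of rating at a point that also carries an ECG requiring at least 10 minutes of rest (Section 6.4.7.1), plus one extra rating per patient if the pre-infusion option is chosen.

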6.5 Patient reported outcomes

The patient-reported outcomes of QIDS-SR-16 and SDS are discussed in Sections 6.2.2.1 and 6.3.2.2, respectively.

6.6 Pharmacokinetics

For timing of individual samples, refer to Table 9. The actual date and time of dosing and sample collection must be recorded on the appropriate eCRF page.

